18.0 APPENDIX

18.1 **S1415CD** List of Protocol Approved Regimens

CLOSED EFFECTIVE 04/15/2020

18.1 **S1415CD** List of Protocol Approved Regimens

a. **Concurrent Radiation is not allowed**

Regimens with concurrent radiation will not be addressed by TrACER as radiation is a contraindication for primary prophylactic growth factors. Patients undergoing concurrent radiation and order templates that include concurrent radiation (e.g. carboplatin/PACLitaxel + XRT) should NOT be considered for this study.

b. **Sequential Regimens**

Sequential regimens (e.g. AC-> T) will not be addressed jointly by TrACER. Eligibility should be determined based solely on the first regimen administered to a patient regardless of subsequent regimens (e.g. by AC only in the sequence AC-> T).

c. **Determining Chemotherapy Order Eligibility**

When determining which regimens to target in the existing EMR/paper order system, the practice should include regimens that are identified in its system as targeting breast, non-small cell lung, or colorectal cancer only, or in the absence of a disease-specific counterpart, either any superset of these diseases (e.g. lung is a superset of non-small cell lung) or no specified disease site. See [Table 1](#) below.

Table 1: EXAMPLES for Determining Chemotherapy Order Eligibility

STUDY REGIMEN (from Table 3)	CHEMOTHERAPY ORDER IN SYSTEM	CHEMOTHERAPY ORDER ELIGIBLE FOR STUDY	RATIONALE
NSCLC CARBOplatin/ etoposide	NSCLC carboplatin/etoposide	Yes	NSCLC is the specific disease targeted by this study
NSCLC CARBOplatin/ etoposide	SCLC carboplatin/etoposide	No	NSCLC is not a type of SCLC
NSCLC CARBOplatin/ etoposide	LUNG carboplatin/etoposide (NSCLC carboplatin/etoposide NOT in system)	Yes	NSCLC is a type of lung cancer and there is no other regimen with these same agents specifically targeting NSCLC
NSCLC CARBOplatin/ etoposide	Carboplatin/etoposide (NSCLC carboplatin/etoposide NOT in system)	Yes	No specific disease targeted and there is no other regimen with these same agents specifically targeting NSCLC
NSCLC CARBOplatin/ etoposide	LUNG carboplatin/etoposide (NSCLC carboplatin/etoposide in system)	No	There is another regimen in the system with these same agents specifically targeting NSCLC. In this case, only

Table 1: EXAMPLES for Determining Chemotherapy Order Eligibility

STUDY REGIMEN (from Table 3)	CHEMOTHERAPY ORDER IN SYSTEM	CHEMOTHERAPY ORDER ELIGIBLE FOR STUDY	RATIONALE
			NSCLC regimen that matches the regimen listed in Table 3 is eligible for the study.
BREAST Gemcitabine	BREAST gemcitabine	Yes	Breast cancer is the specific disease targeted by this study
BREAST Gemcitabine	OVA gemcitabine	No	Breast cancer is not a type of ovarian cancer

d. **Multiple Chemotherapy Orders**

Determining appropriate CSF standing order defaults across multiple chemotherapy orders is beyond the scope of this study. For this reason, patients on multiple chemotherapy orders to be administered within the very first cycle of chemotherapy (including monoclonal antibodies) are ineligible for participation. See [Table 2](#) below.

Table 2: EXAMPLES for Multiple Chemotherapy Orders

STUDY REGIMEN (from Table 3)	CHEMOTHERAPY ORDER(S) IN SYSTEM	CHEMOTHERAPY ORDER ELIGIBLE FOR STUDY	RATIONALE
BREAST TC	Order 1: BREAST TC starting 1/1/2016	Yes	All agents in the regimen are included in one order
BREAST TC	Order 1: docetaxel starting on 1/1/2016 Order 2: cyclophosphamide starting on 1/1/2016	No	The agents that make up the regimen are ordered separately; the study does not support multiple regimen orders.
BREAST PACLitaxel weekly + trastuzumab	Order 1: BREAST paclitaxel weekly + Trastuzumab, cycle 1 starting 1/1/2016	Yes	All agents that make up the regimen are in the same order
BREAST PACLitaxel weekly + trastuzumab	Order 1: BREAST paclitaxel weekly, cycle 1 starting 1/1/2016 Order 2: Trastuzumab, cycle 1 starting 1/1/2016	No	The agents that make up the regimen are ordered separately; the study does not support multiple regimen orders.

e. **For Intervention Arm Components**

Components should only change those regimens that already exist and are used in their ordering system. No practice is expected to add/remove regimens to/from their system as part of this study.

Regimens should only be modified if they *exactly match* the regimen listed in [Table 3](#) below. Regimens should match in dose, cycle length, and chemotherapy drug(s), including any monoclonal antibodies. All regimens derived from NCCN chemotherapy templates at www.nccn.org. Contact [contact] with questions.

Effective December 2, 2019, only registration of patients on regimens with intermediate FN risk will be allowed for randomized sites (Groups 2, 3 and 4). Off limit regimens are shaded in gray.

TABLE 3

Non- Small Cell Lung Cancer			
Regimen	Cycle Length	FN Risk	
Afatinib	1 day	Low	
Albumin-bound PACLitaxel	21 days	Low	
Bevacizumab	21 days	Low	
CARBOplatin/albumin-bound PACLitaxel	21 days	Low	
CARBOplatin/albumin-bound PACLitaxel + pembrolizumab	21 days	Low	
CARBOplatin/PACLitaxel + pembrolizumab	21 days	Intermediate	
CARBOplatin/DOCETaxel	21 days	Intermediate	
CARBOplatin/etoposide	21 days	Intermediate	
CARBOplatin/gemcitabine	28 days	Intermediate	
CARBOplatin/PACLitaxel + atezolizumab + bevacizumab	21 days	Intermediate	
CARBOplatin/PACLitaxel + bevacizumab	21 days	Intermediate	
CARBOplatin/PACLitaxel	21 days	Intermediate	
CARBOplatin/PEMExred + bevacizumab	21 days	Low	
CARBOplatin/PEMExred	21 days	Low	
CARBOplatin/PEMExred + pembrolizumab	21 days	Low	
CARBOplatin/vinORELBine	21 days	Low	
Ceritinib	1 day	Low	
CISplatin/albumin-bound PACLitaxel + pembrolizumab	21 days	Low	
CISplatin/DOCETaxel	21 days	Intermediate	
CISplatin/etoposide	21-28 days	Intermediate	
CISplatin/gemcitabine	21 days	Low	
CISplatin/gemcitabine + necitumumab	21 days	Low	
CISplatin/PACLitaxel	21 days	Intermediate	
CISplatin/PACLitaxel + pembrolizumab	21 days	Intermediate	
CISplatin/PEMExred + bevacizumab	21 days	Low	
CISplatin/PEMExred	21 days	Low	

Non- Small Cell Lung Cancer		
Regimen	Cycle Length	FN Risk
CISplatin/PEMExred + pembrolizumab	21 days	Low
CISplatin/vinORELBine every 21 days	21 days	Intermediate
CISplatin/vinORELBine every 28 days	28 days	Intermediate
CISplatin/vinORELBine + cetuximab	21 days	Intermediate
Crizotinib	1 day	Low
DOCETaxel	21 days	Intermediate
DOCETaxel + ramucirumab	21 days	Intermediate
Erlotinib	1 day	Low
Etoposide (oral)	28-35 days	Intermediate
Gemcitabine	21-28 days	Low
Gemcitabine/DOCETaxel	21 days	Intermediate
Irinotecan	21 days	Low
PACLitaxel	21-28 days	Low
PEMExred	21 days	Low
Pembrolizumab	21 days	Low
PEMExred + bevacizumab	21 days	Low
VinORELBine	21 days	Low
VinORELBine/gemcitabine	21 days	Low

Colorectal Cancer		
Regimen	Cycle Length	FN Risk
Capecitabine	21 days	Low
Capecitabine + bevacizumab	21 days	Low
CapeOX (XELOX) (capecitabine, oxaliplatin)	21 days	Low
CapeOX (XELOX) + bevacizumab (capecitabine, oxaliplatin)	21 days	Low
Cetuximab	7 days	Low
FLOX (fluorouracil, leucovorin, oxaliplatin)	56 days	Low
Fluorouracil/leucovorin weekly	7 days	Low
Fluorouracil/leucovorin weekly + bevacizumab	7 days	Low
FOLFIRI (leucovorin, fluorouracil, irinotecan)	14 days	Low
FOLFIRI + afilbercept (leucovorin, fluorouracil, irinotecan)	14 days	Low
FOLFIRI + bevacizumab (leucovorin, fluorouracil, irinotecan)	14 days	Low
FOLFIRI + cetuximab (leucovorin, fluorouracil, irinotecan)	14 days	Low
FOLFIRI + panitumumab (leucovorin, fluorouracil, irinotecan)	14 days	Low
FOLFIRI + ramucirumab (leucovorin, fluorouracil, irinotecan)	14 days	Low
FOLFOX4 (leucovorin, fluorouracil, oxaliplatin)	14 days	Intermediate
FOLFOXIRI (leucovorin, fluorouracil, oxaliplatin, irinotecan)	14 days	Low

Colorectal Cancer		
Regimen	Cycle Length	FN Risk
FOLFOXFIRI + bevacizumab (leucovorin, fluorouracil, oxaliplatin, irinotecan)	14 days	Low
Irinotecan	21 days	Low
Irinotecan every 14 days	14 days	Low
Irinotecan + bevacizumab	14 days	Low
Irinotecan every 14 days + afibbercept	14 days	Low
Irinotecan every 14 days + cetuximab	14 days	Low
Irinotecan every 14 days + panitumumab	14 days	Low
Irinotecan every 14 days + ramucirumab	14 days	Low
Irinotecan every 21 days + cetuximab	21 days	Low
Irinotecan + cetuximab + vemurafenib	14 days	Low
Irinotecan + panitumumab + vemurafenib	14 days	Low
IROX (irinotecan, oxaliplatin)	21 days	Low
IROX (irinotecan, oxaliplatin) + bevacizumab	21 days	Low
mFOLFOX6 (leucovorin, fluorouracil, oxaliplatin)	14 days	Intermediate
mFOLFOX6 + bevacizumab (leucovorin, fluorouracil, oxaliplatin)	14 days	Intermediate
mFOLFOX6 + cetuximab (leucovorin, fluorouracil, oxaliplatin)	14 days	Intermediate
mFOLFOX6 + panitumumab (leucovorin, fluorouracil, oxaliplatin)	14 days	Intermediate
mFOLFOX7 (leucovorin, fluorouracil, oxaliplatin)	14 days	Intermediate
Panitumumab	14 days	Low
Roswell Park fluorouracil/leucovorin	56 days	Low
Roswell Park fluorouracil/leucovorin + bevacizumab	56 days	Low
Simplified biweekly infusional fluorouracil/leucovorin	14 days	Low
Simplified biweekly infusional fluorouracil/leucovorin + bevacizumab	14 days	Low

Breast Cancer		
Regimen	Cycle Length	FN Risk
AC every 21 days (DOXOrubicin, cyclophosphamide)	21 days	Intermediate
Ado-trastuzumab emtansine	21 days	Low
Albumin-bound PACLitaxel	21 days	Low
Albumin-bound PACLitaxel every 21 days + trastuzumab	21 days	Low
Albumin-bound PACLitaxel every 28 days + trastuzumab	28 days	Low
Anastrozole + trastuzumab	21 days	Low
CAF (cyclophosphamide [oral], DOXOrubicin, fluorouracil)	28 days	Low
Capecitabine	21 days	Low

Breast Cancer		
Regimen	Cycle Length	FN Risk
Capecitabine + trastuzumab	21 days	Low
CARBOplatin	21-28 days	Low
CARBOplatin + trastuzumab	21-28 days	Low
CARBOplatin/gemcitabine	21 days	Intermediate
CARBOplatin/PACLitaxel every 21 days + trastuzumab	21 days	Intermediate
CARBOplatin/PACLitaxel weekly + trastuzumab	28 days	Low
CEF (cyclophosphamide [oral], epirubicin, fluorouracil)	28 days	Intermediate
CISplatin	21 days	Low
CISplatin + trastuzumab	21 days	Low
CMF Bonadonna (classic) (oral cyclophosphamide, I.V.methotrexate, fluorouracil)	28 days	Intermediate
CMF (IV cyclophosphamide, methotrexate, fluorouracil)	21 days	Intermediate
Cyclophosphamide	28 days	Low
Cyclophosphamide + trastuzumab	28 days	Low
DOCEtaxel every 21 days	21 days	Intermediate
DOCEtaxel every 21 days + pertuzumab + trastuzumab	21 days	Intermediate
DOCEtaxel every 21 days + trastuzumab	21 days	Intermediate
DOCEtaxel weekly	7 days	Low
DOCEtaxel weekly + trastuzumab	7 days	Low
DOCEtaxel/capecitabine	21 days	Intermediate
Dose-dense AC (DOXOrubicin, cyclophosphamide)	14 days	High
Dose-dense PACLitaxel	14 days	High
Dose-dense PACLitaxel + trastuzumab	14 days	High
DOXOrubicin every 21 days	21 days	Intermediate
DOXOrubicin weekly	7 days	Low
EC every 21 days (EPIrubicin, cyclophosphamide)	21 days	Low
EPIrubicin	21 days	Low
EriBULin	21 days	Low
EriBULin + trastuzumab	21 days	Low
Everolimus + exemestane	1 day	Low
FAC (fluorouracil, DOXOrubicin, cyclophosphamide)	21 days	Low
FEC (fluorouracil, epirubicin, cyclophosphamide)	21 days	Intermediate
Gemcitabine	28 days	Low
Gemcitabine + trastuzumab	28 days	Low
Ixabepilone	21 days	Low
Ixabepilone + trastuzumab	21 days	Low
Lapatinib + letrozole	1 day	Low

Breast Cancer		
Regimen	Cycle Length	FN Risk
Lapatinib + trastuzumab	7 days	Low
Lapatinib/capecitabine	21 days	Low
Liposomal DOXOrubicin	28 days	Low
PACLitaxel + bevacizumab	28 days	Low
PACLitaxel every 21 days	21 days	Intermediate
PACLitaxel every 21 days + trastuzumab	21 days	Intermediate
PACLitaxel every 21 days + trastuzumab + pertuzumab	21 days	Intermediate
PACLitaxel weekly	7 days	Low
PACLitaxel weekly + trastuzumab	7 days	Low
PACLitaxel weekly + trastuzumab + pertuzumab	7 days	Low
PACLitaxel/gemcitabine	21 days	Low
Palbociclib + fulvestrant	28 days	Low
Palbociclib + letrozole	28 days	Low
Pertuzumab + trastuzumab	21 days	Low
TAC (DOCEtaxel, DOXOrubicin, cyclophosphamide)	21 days	High
TC (DOCEtaxel, cyclophosphamide)	21 days	High
TC + trastuzumab (DOCEtaxel, cyclophosphamide)	21 days	High
TCH (DOCEtaxel, CARBOplatin, trastuzumab)	21 days	High
TCH + pertuzumab (DOCEtaxel, CARBOplatin, trastuzumab)	21 days	High
Trastuzumab	21 days	Low
VinORELBine	7 days	Low
VinORELBine every 21 days + trastuzumab	21 days	Intermediate
VinORELBine + trastuzumab	7 days	Low

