What a physician will see if they prescribe an intermediate risk regimen depends on their study arm. If a component is randomized to include standing orders for PP-CSF for all intermediate risk regimens, default PP-CSF orders will appear on the screen in the same way as the default orders for high-risk regimens. If a component is randomized to not include standing orders for PP-CSF for intermediate-risk regimens, the screen will function in the same way as for low-risk regimens. The alert text will be modified to be specific to the intermediate risk classification of the regimen and the randomized assignment.

Order System- Paper

Paper ordering systems will have the same basic design as the EMR modification but will differ in the implementation strategy, as shown below in [Figure 4](#).

INCLUDE CSF by default
 
DOSE-DENSE AC HIGH risk of FN; PP-CSF recommended
 
Height: _____ Weight: _____
 
Chemotherapy Orders:
 
Doxorubicin 75 mg/m² x _____ m²= _____ mg Cyclophosphamide 600 mg/m² x _____ m² = _____ mg
 
Growth Factors: Pegfilgrastim 6 mg subcutaneous
 
Additional Orders: Saline 1000 mL
	
EXCLUDE CSF by default
 
VINORELBINE LOW risk of FN; PP-CSF not recommended
 
Height: _____ Weight: _____
 
Chemotherapy Orders:
 
Vinorelbine 25 mg/m² x _____ m²= _____ mg
 
Additional Orders: Saline 1000 mL

---	--

[Figure 4](#)

The treating physician may change an individual patient's orders from what is specified by following standard procedures for changing a prescription order when adding or removing CSF. The specific procedures will depend on the EMR and local component preference.

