Sample size estimates for the intermediate risk group are based on a 50% reduction in the FN rate (the reduction observed in trials for high risk settings). This translates to a reduction in FN rate from 15% to 7.5%, when comparing intermediate risk control arm patients (no PP-CSF) to intermediate risk intervention arm patients (PP-CSF). We believe this is reasonable because the one prospective trial evaluating PP-CSF for intermediate risk chemotherapy given to women with breast cancer achieved a risk reduction of 90%, and a systematic review of clinical trials of PP-CSF use in several settings found an FN rate reduction ranging from 17% to 78%. (49) To account for possible correlation between patients within components we estimate an intraclass correlation coefficient (ICC) of 0.02. An ICC of zero corresponds to randomization of individuals rather than components; $ICC > 0$ indicates patient outcomes are more similar within a component than across components. We estimated the ICC for FN in the SWOG adjuvant breast cancer study **S0221** which has 262 clinics with 2,666 patients. (50) Using a random effects logistic regression program (component is the random effect) followed by numerical integration, the ICC was estimated to be 0.01 although statistically significantly greater than zero. We are using 0.02 to protect against underestimation of the ICC. Based on a two-sided 0.05 alpha level test, 24 components in the Intervention arm (12 components randomized to PP-CSF and 12 components to no PP-CSF among intermediate risk patients) and 45 intermediate-risk patients per component on average will give 80% power to detect whether PP-CSF reduces FN rate by 50% among patients receiving intermediate risk chemotherapy. We assume that high, intermediate and low risk patients comprise 30%, 50% and 20% at each component, respectively; this translates to a total of 90 patients per component on average. (51,52)

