Step 2: Consider the hypothesis of [Primary Objective b](#): a relative reduction in FN occurrence over 6 months from registration between the Intervention and Usual Care arms (measured by the odds ratio) over both high and intermediate risk groups. We assume FN risk of 25% for the high risk chemotherapy group (translating to a reduction in FN rate from 25% to 12.5%). Using the sample size calculations from Step 1, we employ a 3:1 randomization scheme in the main trial, resulting in 8 components randomized to Usual Care and 24 components randomized to Intervention. This translates to a total of 2,880 patients, 32 components (90 patients per component on average) for the study, and gives us 90% power for [Primary Objective b](#): to detect a 50% reduction in FN events among high and intermediate risk patients in components randomized to the guideline-based PP-CSF order Intervention vs. Usual Care. [Figure 1](#) displays a power curve for our first and second Primary Objectives.

[figure not shown]

Figure 1: Power with respect to the reduction in FN rate. The dashed vertical line is at 50% reduction. The two dashed horizontal lines are at 80% and 90% power.

Table 2 below illustrates how the required sample size for [Primary Objective c](#) and corresponding power for [Primary Objective a](#) vary according to the ICC.

Table 2. Power to detect 50% relative reduction in the FN rate. Power depends on control arm event rate and ICC.

Intra-Class Correlation	Total Sample Size	Per arm sample size		Per arm # of components		Per component sample size		Power	
		Usual Care	Order Entry	Usual Care	Order Entry	Usual Care	Order Entry	Primary Obj b	Primary Obj a
0	1536	384	1152	8	24	48	48	80%	98%
.01	1984	496	1488	8	24	62	62	80%	94%
.02	2880	720	2160	8	24	90	90	80%	90%
.03	5376	1344	4032	8	24	168	168	80%	86%

Using this sample size and with greater than 80% power, we can detect the following effect of Intervention versus Usual Care in the process outcomes of [Primary Objective a](#), namely the proportions of patients using CSF as primary prophylaxis versus other use: a reduction in CSF use from 17% to 7% among low risk patients and an increase in CSF use from 40% to 75% among high-risk patients (based on observed use in our prior observational study). (53)

In addition to the 32 study components, we will include 13 components with existing PP-CSF order entry systems in the parallel cohort to recruit 720 patients (56 patients per component on average).

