In a secondary analysis, we will do a three-way comparison among the intermediate risk patients, comparing Usual Care to each of the two Intervention groups – PP-CSF and no PP-CSF. For this analysis, we will fit a similar model as above, but instead of an indicator variable for randomized group (Intervention versus Usual Care), we will include a categorical variable for randomized group with three levels: (i) Usual Care (reference), (ii) Intervention – PP-CSF, and (iii) Intervention – no PP-CSF.

Subgroup analysis: We will assess the magnitude of intervention effect in subgroups and how that effect changes across subgroups (after stratification by subgroup). We will use interaction tests and construct a forest plot to display the heterogeneity in intervention effects across subgroups (details in [Section 11.7](#)). Subgroup analyses will be performed for each cancer type, level of FN risk, race and the following variables: race (African-American, white, other); age (categorized as < 50, 50-59, 60-69, 70-79, 80+ years); non-cancer comorbidity performance status (Zubrod), stage of cancer at enrollment (distant, local, regional). (54, 55, 56, 57, 58, 59)

c. *Primary Objective c: To compare the rate of FN among intermediate risk patients registered to Intervention components by component treatment assignment (administer PP-CSF to intermediate risk patients versus not).*

The rate of FN will be evaluated at 6 months post-registration. The risk of FN is greatest during the first cycle, but patients are still at risk throughout therapy. The FN risk levels assigned to the various systemic therapies in this protocol are based on risk for the duration of treatment, and so the analysis will look at the FN rate at 6 months into therapy.

As before, since patients are nested within components, a mixed effects logistic model with a random effect for component will be used to assess the effect of prescribing CSFs as primary prophylaxis on FN occurrence within 6 months from registration. In addition to including an indicator variable for randomized group (CSFs prescribed as primary prophylaxis or not), we will adjust for component-level characteristics and patient-level clinical and demographic variables.

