11.7 Heterogeneity of Treatment Effect

Heterogeneity of treatment effect is routinely shown using interaction tests and forest plots of the odds ratio (or hazard ratio) and 95% CI for each relevant subgroup. For the primary outcomes, we will use forest plots to assess the magnitude of intervention effect in subgroups (after stratification) and how that effect changes across subgroups. The interaction of intervention and each factor will also be tested in the model after the main effects have been included. The scientific plausibility of that subset effect will be assessed only if there is evidence of statistically significant interaction. In the absence of a significant main effect, it is likely that most effects in a subset are spurious and should not be regarded as meaningful. If there is a significant overall main effect, but certain subgroups do not share that effect as evidenced by an odds ratio close to unity that might suggest heterogeneity. Interest lies in interactions that may result in different treatment decisions for different subgroups. This translates to a greater interest in qualitative interactions (treatment effects among subgroups differ in direction) than quantitative interactions (treatment effects differ in magnitude but not in direction). While a significant interaction shows if subgroups are different from each other, it could miss qualitative interactions. Forest plots show the treatment effect estimates and variability within each subgroup. They will be used as a complementary visual tool for assessing both qualitative and quantitative interactions.

We expect the relative effect (but not the absolute effect) of Intervention versus Usual Care to be the same in high and intermediate patients. This will be tested by an interaction term, but there is already a separate planned analysis for the intermediate group alone that has 80% power. Additionally, there is a planned analysis of CSF use as primary prophylaxis in the high and low risk groups that has >80% power. No other a priori hypotheses are stated, and therefore all other subgroup analyses are exploratory.

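### Objective b's cancer-type interaction is confounded with FN risk level, because every High-risk regimen in Table 3 is a breast regimen, and it may show a spurious tumour difference

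*Combined protocol and SAP*

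**What the plan says.** Section 18.1, Table 3, assigns each regimen a risk level. The High rows, such as "Dose-dense AC (DOXOrubicin, cyclophosphamide) 14 days High", all stand under breast cancer.

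Section 7.2 makes the intervention depend on that level. CSF is in the order by default for High and out by default for Low. For Intermediate it depends on a second randomization: "If a component is randomized to not include standing orders for PP-CSF for intermediate-risk regimens", the screen behaves as it does for Low. Section 11.1 puts 12 Intervention components in each of these two groups.

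For Objective b, Section 11.2 states: "Subgroup analyses will be performed for each cancer type, level of FN risk, race and the following variables". Section 11.7 gives the method: "The interaction of intervention and each factor will also be tested in the model after the main effects have been included". It names no intervention-by-risk term for the cancer-type test and does not mention that the two factors overlap. It also states: "We expect the relative effect (but not the absolute effect) of Intervention versus Usual Care to be the same in high and intermediate patients". That expectation will be tested by an interaction term. Apart from this and the planned analyses by risk group, "all other subgroup analyses are exploratory".

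**The concern.** High-risk patients can appear only in the breast stratum. The breast odds ratio for Intervention versus Usual Care therefore averages a High and an Intermediate effect, while the lung and colorectal odds ratios contain no High effect. Adjusting for risk level as a main effect corrects baseline FN rates. It does not correct an intervention effect that itself varies by risk level.

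The design makes such variation plausible. All 24 Intervention components default to PP-CSF for High patients, but only 12 of the 24 do so for Intermediate patients. If the effect does vary, the forest plot and the interaction test could suggest that the order system works better in breast cancer, when the cause is which regimens Table 3 calls High.

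The overlap also runs the other way: the planned High-versus-Intermediate interaction compares breast-only patients with a three-tumour mix. And although the Background (Section 2.0) cites 1.5% PP-CSF use among lung cancer patients on high-risk chemotherapy, the high-risk results can inform breast cancer only.

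**Working it through.** **Regimen counts, Table 3**

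| Tumour | Low | Intermediate | High | Total |
|---|---|---|---|---|
| NSCLC | 26 | 18 | 0 | 44 |
| Colorectal | 33 | 6 | 0 | 39 |
| Breast | 43 | 16 | 8 | 67 |

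**Inputs from Section 11.1.** 8 Usual Care and 24 Intervention components with 90 patients each (720 and 2,160); 30% High, 50% Intermediate, 20% Low; ICC 0.02; two-sided alpha 0.05. For High: "We assume FN risk of 25% for the high risk chemotherapy group (translating to a reduction in FN rate from 25% to 12.5" per cent. For Intermediate, PP-CSF against no PP-CSF: "This translates to a reduction in FN rate from 15% to 7.5" per cent. High-risk CSF use: 40% in Usual Care, 75% under Intervention.

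**Assumed, not in the documents.** The breast share of Intermediate patients (20–80%), Usual Care PP-CSF use in Intermediate patients (0–50%) and, where Low patients enter, a Low FN rate of 5% with 40% breast.

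**The plan's own power.** Objective c: design effect 1 + 44 × 0.02 = 1.88; effective size 540/1.88 = 287 per group; 15% versus 7.5% gives 81.3% (79.8% on the log-odds scale) against the stated 80%. Objective b with all patients and Low at 5% in both arms: 16% versus 8.5%, design effect 1 + 89 × 0.02 = 2.78, power 90.2% against the stated 90%. The plan gives no figure for the cancer-type test.

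**Model for the check.** Logistic regression with arm, breast, arm × breast and a High main effect, in High and Intermediate patients. Within each risk level the effect is identical in every tumour, so any arm × breast signal is false.

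*A. Planned rates applied to both levels.* High OR = (0.125/0.875)/(0.25/0.75) = 0.429. Intermediate OR = (0.075/0.925)/(0.15/0.85) = 0.459. The ratio of breast to non-breast odds ratios is 0.95–0.96 and rejection is 5.1–5.5%, that is, nominal.

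*B. Intermediate diluted by half, High not.* This takes no PP-CSF use in Usual Care Intermediate patients and full adherence to defaults. Mean Intermediate rate under Intervention = (15 + 7.5)/2 = 11.25%, so OR = (0.1125/0.8875)/(0.15/0.85) = 0.718. By hand at a 40% breast share:
- High (216 and 648 patients): variance of log OR = 1/40.5 + 1/70.9 = 0.0388.
- Intermediate breast (144 and 432): 1/18.4 + 1/43.1 = 0.0777.
- Intermediate non-breast (216 and 648): 1/27.5 + 1/64.7 = 0.0518.
- Precision-weighted breast log OR = (25.8 × −0.847 + 12.9 × −0.331)/38.7 = −0.675, so OR is about 0.51 against 0.72.
- z = (−0.675 + 0.331)/√(1/38.7 + 0.0518) = −0.344/0.279 = −1.24, so rejection is about 23%.

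Over breast shares of 20–80%, the fitted breast OR is 0.48–0.56, the ratio 0.67–0.78, and rejection falls from 34% to 9%. Simulation with component effects gives 34%, 23% and 16% at shares of 20%, 40% and 60%. A separate simulation of the three-tumour test (2 df) gives 23%, 16% and 10%.

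*C. Dilution on both sides.* Take 25% and 15% as rates without PP-CSF, and let PP-CSF halve FN. High: 25 × (1 − 0.5 × 0.40) = 20% in Usual Care, 25 × (1 − 0.5 × 0.75) = 15.6% under Intervention, OR about 0.74. With Usual Care Intermediate use from 0 to 50%, the Intermediate OR runs from 0.72 to 1.00, the breast to non-breast ratio from 1.03 to 0.78, and rejection is 5–14%.

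*D. Low patients included in A.* The Section 11.2b model is not explicitly restricted to High and Intermediate, although Step 2 of Section 11.1 frames the hypothesis in those groups. With Low at 5% in both arms, the ratio is 0.75–0.90 and rejection 7–13%.

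**With the extra term.** Adding arm × risk to B gives a ratio of 1.00 and 5.0% rejection at every breast share. The standard error of the log ratio is then 0.36–0.44. At a 40% share it is √(1/18.4 + 1/43.1 + 1/27.5 + 1/64.7) = 0.36, against 0.28 without the term.

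**The case against.** A reader might infer that the cancer-type test will report a tumour difference even when the effect is the same in every tumour. The documents do not support that. Unequal risk mix biases the contrast only if the intervention effect differs by risk level, and Section 11.7 expects equal relative effects. Even under B, most trials would show no significant interaction.

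B is also one-sided. The 15% to 7.5% figure compares PP-CSF with no PP-CSF inside the Intervention arm; Section 11.1 does not plan an unchanged rate against Usual Care at half the components. If Intermediate is diluted, the plan's 40% to 75% use rates dilute High too. Reading 25% as the Usual Care rate, High falls to 25 × 0.625/0.80 = 19.5%, OR about 0.73, close to the diluted Intermediate 0.72. This stands, and it is why C belongs beside B.

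Section 11.7 has safeguards: subgroup analyses of this kind are exploratory, plausibility is considered only after a significant interaction, and interest is greater in effects that change direction. The artefact here is a difference in size, not direction. These points limit the consequence but do not remove the confounding, and the forest plot will be read whatever the p-value.

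Risk level has its own planned interaction test, and Section 11.2b adds a three-way comparison in Intermediate patients. Neither changes the cancer-type model. Finally, from December 2, 2019 randomized sites could register Intermediate patients only (Section 5.2), so the actual High share may be below the 30% used here.

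**Conclusion.** The point holds in a limited form. That all eight High regimens are breast regimens, and that the cancer-type model lacks an intervention-by-risk term, is plain from the documents. Whether a false tumour difference follows depends on whether the intervention effect differs by risk level.

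In High and Intermediate patients, false rejection is essentially nominal if the relative effects are equal; about 5–14% when the plan's High-risk use rates are applied and Usual Care Intermediate use is 0–50%; and about 10–34%, at breast shares of 20–60%, if Intermediate is diluted by half and High is not. The breast share and Usual Care use in Intermediate patients are assumptions, so these are ranges and not predictions.

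Only an exploratory analysis is at risk; the primary tests are unaffected. The restriction of high-risk conclusions to breast cancer does not depend on any of these assumptions.

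**What to change.** In Sections 11.2b and 11.7:
- Add the intervention-by-FN-risk-level term to the Objective b cancer-type interaction model, or run the cancer-type subgroup analysis in intermediate-risk patients only.
- Repeat the High-versus-Intermediate interaction within breast cancer patients as a sensitivity check.
- State that the high-risk results of Objectives a and b apply to breast cancer only.

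Nothing in Table 3 or in the check above calls for the same term in the other Objective b subgroup models.

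The cost is SAP wording and one model term, with no new data. The downside is precision: High patients no longer inform the cancer-type contrast, so its confidence interval widens.
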